4.2.3. Safety Analysis Set

Safety analysis set (SS): all patients who have taken at least one dose of study drug. Safety analyses will be based on the SS by actual treatment received.

4.2.4. Pharmacokinetic Analysis Set

PK Analysis Set (PKS): All patients who received at least one dose of the study drug and had at least one valid concentration data of the tested components after drug administration. Pharmacokinetic analyses will be based on the PKS.

Patients will be excluded from the PK analysis set if they had major protocol deviations, inaccessible or incomplete data, or other circumstances that could affect the pharmacokinetic analysis. The list of patients with any major deviation or event significantly affecting PK results and reasons for exclusion should be reviewed and confirmed before database lock.

4.3. Study Population

4.3.1. Subject disposition

The distribution of patients will be summarized based on all screened patients, including patient screening, enrolled medication, reason for end of treatment, reason for withdrawal from the study and inclusion in each analysis set, and listing will be provided in detail.

4.3.2. Protocol Deviations

The number and percentage of patients with major protocol deviations (including major deviations from inclusion and exclusion criteria) during the trial will be summarized, and the reasons for major protocol deviations will be summarized and listed in detail. Patients with multiple major protocol deviations in different categories will be counted in each corresponding category.

4.3.3. Demographic and Baseline Characteristics

Demographic and baseline disease characteristics include age at the time of informed consent, age group (18-65, >65-75, >75), gender, vital signs (weight, height, body surface area) at screening, ECOG score, presence of brain metastasis, baseline lactate dehydrogenase (LDH) level, family history, allergic history, smoking history, tumor history and history of tumor radiotherapy.

Confidential

Descriptive statistics (mean, standard deviation, median, range, etc) will be used to summarize continuous variables, and frequency and percentage will be used to summarize categorical variables.

4.3.4. Previous Medical History, Prior Medications, and Non-Drug Therapies

Previous medical history will be coded using the latest version of the Medical Dictionary for Regulatory Activities (MedDRA Chinese version 24.0) and summarized by System Organ Class (SOC) and Preferred Term (PT). Listing will be provided in detail.

Prior medications or therapies is defined as any non-study medications or therapies administered by the patient from 14 days prior to signing informed consent through the first dose of study drug. Patients' prior medications will be coded using the latest version of the World Health Organization Drug Dictionary (WHO-DD (March 2021) Chinese version) and will be summarized by chemical subgroup and generic drug name. Listing will be provided in detail.

4.3.5. Concomitant Medications and Non-Drug Therapies

Concomitant medications will be coded using the latest version of WHO-DD and summarized by chemical subgroup and generic drug name, and the number and percentage of patients using concomitant medications will be counted. Concomitant medications and concomitant non-drug therapies will be presented in detail in listings.

The number of cycles with interleukin (IL-11) and thrombopoietin (TPO) administration and the weekly event rate will be summarized and tabulated in detail by patient, respectively.

4.3.6. Subsequent antineoplastic therapy

Subsequent antineoplastic therapy refers to any subsequent non-study oncology agent administered after the first dose of study drug. Subsequent anticancer therapies will be coded using the most recent version of the World Health Organization Drug Dictionary (WHODrug) and summarized by chemical subgroup and generic drug name. The number and percentage of subjects with subsequent anticancer therapy will be summarized by treatment group. Listing will be provided in detail.

4.4. Efficacy analysis of myeloprotection

The efficacy analysis of Trilaciclib for myeloprotection in ES-SCLC patients will be based primarily on the Full Analysis Set (FAS). If the number of patients differed by more than 10% between the PPS and the FAS, efficacy analyses based on the PPS for myeloprotection could be performed to support efficacy analyses for the primary and key secondary endpoints.

4.4.1. Primary Efficacy Endpoint

The primary efficacy endpoint is the duration of severe neutropenia (DSN) during Cycle

1. DSN will be assessed by treatment group using two different strategies. Strategy 1 is the primary analysis and Strategy 2 is the supportive sensitivity analysis. DSN derivation in each strategy will include any unscheduled data and use the actual assessment date (non-visit date).

4.4.1.1. Strategy 1: Missing ANC values not imputed

For patients who experienced at least 1 episode of severe neutropenia (SN) within each cycle, a DSN is defined as the number of days from the date of the first absolute neutrophil count (ANC) value $< 0.5 \times 10^{9}$ /L in that cycle to the date of the first ANC value $\ge 0.5 \times 10^{9}$ /L that met the following requirements: (1) occurred after an ANC value $< 0.5 \times 10^{9}$ /L, and (2) no other ANC value $< 0.5 \times 10^{9}$ /L occurred between that date and the end of that cycle (otherwise the SN event is considered not resolved at the end of that cycle). If a patient does not experience any SN during the cycle, DSN will be counted as 0 for that cycle. Exceptions will be handled using the following rules:

- If the SN event is not resolved at the end of the cycle, the DSN will be calculated as above, but the end date is the end date of the cycle;
- If a patient dies during the period of the SN event, the DSN will be calculated as described above, but the end date is the date of death;
- If a patient withdraws consent or is lost to follow-up during the period of the SN event, the DSN will be calculated as described above, but the end date will be the last ANC assessment date before the end of the study.

Nonparametric analysis of covariance (Nonparametric ANCOVA) will be used to evaluate DSN-based differences in efficacy between the test and placebo groups. The nonparametric covariance model will include covariates of baseline ANC study value as a continuous variable, and fixed effects of number of lines of treatment (1st line versus 2nd/3rd line), ECOG (0 or 1 versus 2), brain metastases (yes versus no), and treatment arm (Trilaciclib versus placebo) as categorical variables. Stratification will be combined or reduced appropriately if the number of patients within a stratum is small. The p-value for the 2-sided test will be calculated from the model, and it will be provided the difference in means between the two treatment groups and its 95% confidence interval (CI) based on Satterthwaite t-test, as well as the median difference between the groups and its 95% confidence interval estimated using Hodges-Lehmann.

In addition, DSN will be summarized for each cycle by treatment group using descriptive statistics.

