The downstream target of CDK4/6 is the retinoblastoma (Rb) protein, which is phosphorylated upon CDK4/6 activation to allow cells to enter S phase. CDK4/6 inhibitors arrest cells in G1 phase by inhibiting downstream pathways dependent on functional Rb protein. It has been shown that SCLC is universally inactivated by tumor protein-53 (TP53) and retinoblastoma protein-1 (RB-1), so it is basically believed that functional Rb protein is almost absent in SCLC. In addition, two recent reports have described the genomic profile of SCLC in detail using next generation sequencing methods, including complete exome sequencing, transcriptome profiling by RNA sequencing (RNASeq), copy number analysis as well as limited whole genome sequencing to identify translocations. These reports confirm the conjecture raised in previous studies based on small numbers of tumor samples that inactivation of driver mutations TP53 and RB-1 commonly occurring in SCLC. Consistent with these findings, preclinical in vitro and in vivo studies have shown that Trilaciclib administered prior to chemotherapy does not attenuate the killing of RB-1 inactive tumors, including SCLC. Thus, SCLC can be considered CDK4/6-independent due to near universal RB-1 inactivation, which makes selective protection of HSPCs without compromising the antitumor efficacy of chemotherapy a potentially viable therapeutic strategy.

Three randomized, double-blind Phase 2 clinical trials in patients with small cell lung cancer (SCLC) demonstrated that Trilaciclib administered in combination with chemotherapy (including 1st line, 2nd/3rd line) prevented or mitigated chemotherapy-induced myelosuppression. The G1T28-05 and G1T28-02 studies showed that Trilaciclib administered before first-line chemotherapy (carboplatin combined with etoposide) reduced the duration of severe neutropenia in Cycle 1 from 4 days and 3 days to 0 days, and the occurrence of severe neutropenia from 49.1% and 42.1% to 1.9% and 5.1%, respectively; the G1T28-03 study results showed that the use of Trilaciclib before topotecan reduced the duration of severe neutropenia in Cycle 1 from 7 days to 2 days, and the occurrence of severe neutropenia from 75.9% to 40.6%.

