2.2. Sample Size Determination

The sample size of the second part of this study needs to meet the need to test the efficacy of DSNs in Cycle 1 and is calculated by stochastic simulation. An integrated analysis of the three overseas pivotal studies of Trilaciclib in SCLC showed an approximately 4-day reduction in Cycle 1 DSN in the Trilaciclib group relative to the placebo group. Taking into account the derivation of DSN in Cycle 1, DSN in Cycle 1 is 0 if the subject did not experience any SN during Cycle 1. When there is a large proportion of zero-values, i.e., a large proportion of subjects who do not have any SNs in Cycle 1, the Cycle 1 DSNs more closely follow a Poisson distribution with a mean of -log (proportion of subjects who do not have any SNs in Cycle 1). In the integrated analysis, the proportion of subjects who developed SN during Cycle 1 is 6.7% in the Trilaciclib group compared to 49.6% in the placebo group. Assuming that the proportion of subjects in this study who occurred SN during Cycle 1 is 10% in the Trilaciclib group and 45% in the placebo group, the means of Poisson distributions is 0.105 and 0.598 for the corresponding Trilaciclib and placebo groups, respectively. The stochastic simulation is repeated 10,000 times, each time obtaining the DSN in Cycle 1 from a Poisson distribution and performing comparison between groups by Mann-Whitney-Wilcoxon test, 70 subjects (35 per group) provided approximately 95% power at the test level of $\alpha = 0.05$ (2-sided). Assuming a dropout rate of 12%, the sample size for Part II is 80 subjects (40 per group).

3. Study Conduct

The second part of this study is a randomized double-blind, placebo-controlled study enrolling approximately 80 patients with ES-SCLC, stratified by 1st line vs 2nd/3rd line ES-SCLC, ECOG PS (0-1 vs 2), and presence vs absence of brain metastases, randomized in a 1:1 ratio to Trilaciclib versus placebo where 1st line ES-SCLC patients receive Trilaciclib/placebo in combination with EC regimen (Trilaciclib-EC group and placebo-EC group), 2nd/3rd line ES-SCLC patients will receive Trilaciclib or placebo in combination with Topotecan (Trilacicli-TPT group and placebo-TPT group), and the efficacy of Trilaciclib (prevention of

myelosuppression) will be evaluated with duration of severe neutropenia (DSN) in Cycle 1 as the primary endpoint.

4. Statistical Analysis Methods

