4.4.2.1. Incidence of serious neutropenia events

The total number of SN events is the total number of cycles with at least one ANC value $< 0.5 \times 10^{9}$ /L. For example, two ANC values less than 0.5 x 10⁹/L during Cycle 2 are counted as only one SN event. If a patient does not experience any SN events, the number of SN events for that patient will be counted as zero. Unscheduled data will be included and and actual SN assessment date (non-visit date) will be used. Whether a patient experienced a SN event is a binary variable (yes or no); 'yes' if ≥ 1 cycles with a SN event is observed; and 'no' otherwise.

SN events will be summarized by treatment group using descriptive statistics. Part 2 of the study will analyze the adjusted rate ratio (aRR) between the two treatment groups based on a modified Poisson regression model. The model includes baseline ANC measurement as covariate and IRT-based randomization stratification factors including number of lines of therapy (1st line versus 2nd/3rd line), ECOG (lines 0-1 versus 2) (not included in the actual analysis), and brain metastases (yes versus no), as well as treatment arm as fixed effects. Logarithmic transformed values of the number of cycles will be included in the modeling as offset variables. P-values, aRR (Trilaciclib versus placebo) and their 95% CIs will be provided for the 2-sided tests. In addition, Cochran-Mantel-Haenszel (CMH) weights will be used to calculate the adjusted rate difference between the two arms (Trilaciclib versus placebo) and its 95% CI in Part 2 of the study, and stratified exact CMH method will be used to calculate P values under the 2-sided test according to IRT-based randomization stratification factors to test the stability of the analysis results.

4.4.2.2. Incidence of red blood cell transfusion events occured on/after Week 5

Each red blood cell (RBC) transfusion (including whole blood transfusion and each red blood cell component) occured on/after Week 5 is defined as a separate event and included in the efficacy analysis. Whether a patient experiences a RBC transfusion event is defined as a binary variable (yes or no); "yes" if a total number of RBC transfusion events ≥ 1 is observed, otherwise "no".

The statistical analysis method is similar to that described for SN incidence in Section 4.4.2.1, except hemoglobin (HGB) baseline measurement will be used as covariate instead of

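### Cycle 1 DSN: the primary test is covariate-adjusted, but the only estimate in days is not, and the accompanying Hodges-Lehmann difference is 0 whenever fewer than half of each arm has severe neutropenia

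*SAP*

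**What the plan says.** SAP 4.4.1.1 (Strategy 1, the primary analysis) counts DSN as 0 for a patient with no SN in the cycle. "The nonparametric covariance model will include covariates of baseline ANC study value as a continuous variable", and line of treatment, ECOG, brain metastases and arm enter as fixed effects; small strata may be combined. The two-sided p-value comes from that model.

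Two effect estimates follow. One is "the difference in means between the two treatment groups and its 95% confidence interval (CI) based on Satterthwaite t-test". The other is introduced by "as well as the median difference between the groups and its 95% confidence interval estimated using Hodges-Lehmann". No covariate or stratum is attached to either. Protocol 10.3.4 plans the mean difference with a Satterthwaite interval and does not mention Hodges-Lehmann.

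For the key secondary SN endpoint, SAP 4.4.2.1 does plan adjusted estimates: a rate ratio from a regression model, and "Cochran-Mantel-Haenszel (CMH) weights will be used to calculate the adjusted rate difference between the two arms (Trilaciclib versus placebo) and its 95% CI".

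SAP 2.2 assumes Cycle 1 SN in "10% in the Trilaciclib group and 45% in the placebo group", and cites "6.7% in the Trilaciclib group compared to 49.6% in the placebo group" from the integrated analysis of the overseas studies.

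**The concern.** There are two separate weaknesses in how the primary effect would be described.

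- **Estimate and test do not match.** The p-value uses the stratification factors and baseline ANC. A Satterthwaite t-test is a two-sample unequal-variance method with no place for them. If line of treatment strongly predicts DSN, the interval in days leaves between-line variation in its standard error, although randomisation was stratified by line. A key secondary endpoint would have adjusted estimates while the primary endpoint has none in days. Strategy 2 gives an adjusted hazard ratio, but only among patients who had SN, so it does not fill the gap.
- **Hodges-Lehmann can sit at 0.** It is the median of all between-arm pairwise differences. With many zeros in both arms most pairs may tie, and a clearly significant trial could list a median difference of 0 days with an upper confidence limit of 0.

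What is at stake is the precision and readability of the reported effect.

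**Working it through.** **1. The plan's own figures.** The Poisson means are -ln(0.90) = 0.105 and -ln(0.55) = 0.598. Simulating the Mann-Whitney-Wilcoxon test with 35 per arm gives 94.5-94.9% power, against about 95% stated. For dropout, 70/0.88 = 79.5, so 80. All reproduce.

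**2. When Hodges-Lehmann must be 0.** Take D = trilaciclib minus placebo over all pairs. D < 0 requires that the placebo patient had SN, so the share of negative pairs cannot exceed the observed placebo SN share. D > 0 requires that the trilaciclib patient had SN, so the share of positive pairs cannot exceed that arm's SN share. If both shares are under 50%, the median of D is 0 whatever the episode lengths. No exception occurred in 5,000 random data sets.

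Under the plan's Poisson model the exact shares are 41.7% negative, 52.7% zero and 5.7% positive, so the population value is 0, while the mean difference is 0.105 - 0.598 = -0.49 days.

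**3. How often this happens.** The condition concerns observed shares. At a true placebo rate of 45%, the observed share is under half with probability 0.72 (35 per arm) or 0.68 (40 per arm). The estimate can still be 0 above half, because the negative pairs themselves must reach half. Simulated trials with Wilcoxon p < 0.05, 35-40 per arm:

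| SN, trilaciclib vs placebo | Durations | Hodges-Lehmann = 0 | Upper limit = 0 | Median lower limit |
|---|---|---|---|---|
| 10% vs 45% | plan's Poisson | 84-86% | over 99% | -1 day |
| 6.7% vs 49.6% | assumed 2-14 days | about 60% | about 97% | -5 to -4 days |

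Under the Poisson model both limits are 0 in 21-26% of significant trials.

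The line mix matters, and the documents do not fix it. With assumed SN rates of 5% vs 42% first line and 30% vs 70% later line, the estimate is 0 in 88% of significant trials if all patients are first line, 65% at 70% first line, 45% at 50% and 24% at 30%.

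**4. Width of the mean-difference interval.** Protocol Table 3 gives Cycle 1 DSN mean (SD) as follows. Placebo: 3 (3.9), n = 38, and 4 (4.7), n = 53, first line; 7 (6.2) on topotecan. Trilaciclib: 0 (0.5), n = 39, and 0 (1.0), n = 54, first line; 2 (3.9) on topotecan.

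- First-line placebo mean: (38×3 + 53×4)/91 = 3.58.
- First-line placebo variance: (37×3.9² + 52×4.7²)/89 = 19.23.
- First-line trilaciclib variance: (38×0.5² + 53×1.0²)/91 = 0.69.

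Let f be the first-line fraction, with 40 per arm. In each arm the within-line variance is f×V(first line) + (1-f)×V(topotecan), and the between-line variance is f(1-f)×(difference in line means)².

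At f = 0.5:
- Within-line: placebo 0.5×19.23 + 0.5×38.44 = 28.83; trilaciclib 0.5×0.69 + 0.5×15.21 = 7.95.
- Between-line: placebo 0.25×3.42² = 2.92; trilaciclib 0.25×2² = 1.00.
- SE stratified by line: √((28.83 + 7.95)/40) = 0.96 days.
- SE unadjusted: √((28.83 + 7.95 + 2.92 + 1.00)/40) = 1.01 days.

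| First line | SE unadjusted | SE by line | Reduction |
|---|---|---|---|
| 30% | 1.08 | 1.04 | 3.6% |
| 50% | 1.01 | 0.96 | 4.9% |
| 70% | 0.91 | 0.87 | 5.1% |

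Simulation with DSN matched approximately to Table 3 by line, and an assumed baseline-ANC effect, agrees. The interval is 2.9-5.0% narrower with line and ANC, and 1.7-3.9% narrower with all three strata and ANC. At 50% first line with an ANC odds ratio of 1.5 per SD, the half-width falls from 2.04 to 1.94-1.97 days. Coverage of the adjusted interval is 94.7-95.3%; that of Satterthwaite is about 95.4-96.2%, slightly conservative. With SN at 10% vs 45% in both lines, so that line predicts nothing, the adjusted interval is about 2-3% wider.

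**The case against.** The strongest reply is that nothing here is an error. Zero is the correct value of a correctly named estimator. The Satterthwaite interval is valid under 1:1 randomisation and is what the protocol specifies. Hodges-Lehmann is an SAP-only addition beside it. DSN is also summarised by arm and cycle, and SN incidence has adjusted estimates. The precision gained is 0.07-0.10 day of half-width against an expected effect of about 4 days, and Cycle 1 blood counts are scheduled days apart. All of this stands, and it is why the point is minor. It does not remove the mismatch: the adjustment uses factors already collected and already in the primary model, and the cost is small.

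A reader might infer that Hodges-Lehmann is bound to be 0 at the plan's rates. The documents do not support that. The guarantee depends on observed SN shares, and the estimate is non-zero in 14-16% of significant trials at 10% vs 45% and in about 40% at 6.7% vs 49.6%. SN on placebo plus topotecan was 75.9% in the earlier second/third-line study, though at 1.5 mg/m² rather than this trial's 1.25 mg/m², and that figure is not stated to be for Cycle 1 alone. A topotecan-heavy sample would often give a non-zero value.

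The SAP never uses the word unadjusted. That reading follows from the named t-test and from the p-value alone being tied to the model.

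**Conclusion.** The point holds as a minor matter of precision and reporting. The only planned estimate of the primary effect in days that moves reliably with the effect ignores the covariates of the primary test. Its interval is about 2-5% too wide if line predicts DSN. That size rests on Table 3 carrying over to this trial, on an unknown line mix and, in the simulations, on an assumed ANC effect. The Hodges-Lehmann difference will often be 0 despite a real effect: about 84-86% of significant trials under the sizing model, about 60% at the integrated rates with assumed durations, and less with more topotecan patients.

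Two stronger readings fail. The primary conclusion is not at risk, because the p-value comes from the model and the test, alpha, power and success decision do not depend on either estimate. Nor would the trial lack an effect estimate: the mean difference remains valid, and the Hodges-Lehmann lower limit usually still carries information.

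**What to change.** In SAP 4.4.1.1:

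1. Add a mean difference in days with 95% CI, adjusted for baseline ANC and the same strata as the primary test (with the same pooling where strata are small), using an unequal-variance robust standard error. State which strata enter: SAP 4.4.2.1 marks ECOG as left out of the actual analysis, while 4.4.1.1 includes it.
2. Keep the Satterthwaite interval, labelled as the protocol's unadjusted estimate.
3. Label Hodges-Lehmann supplementary, with a note that ties at 0 can make it 0 despite a real effect.

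A Mann-Whitney probability (0.417 + 0.527/2 = 0.68 under the planning model, unstratified) is optional; if reported, the SAP should say whether it is stratified.

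The cost is SAP wording and a little programming, with no new data. The downside is an adjusted interval about 2-3% wider if line turns out not to predict DSN.

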4.4.1.2. Strategy 2: Missing ANC values not imputed, censored handling unresolved SN

For patients who experienced at least 1 episode of severe neutropenia (SN) within each cycle, a DSN is defined as the number of days from the date of the first absolute neutrophil count (ANC) value $< 0.5 \times 10^{9}$ /L in that cycle to the date of the first ANC value $\ge 0.5 \times 10^{9}$ /L that meet the following requirements: (1) occurred after an ANC value $< 0.5 \times 10^{9}$ /L, and (2) no other ANC value $< 0.5 \times 10^{9}$ /L occurred between that date and the end of that cycle (otherwise the SN event is considered not resolved at the end of that cycle). Patients will not be included in the analysis if they does not experience any SN during this period. Exceptions will be handled using the following rules:

- If the SN event is not resolved at the end of the cycle, the DSN will be calculated as described above, but the end date will be the end date of the cycle or the last contact date, whichever occurs first;
- If a patient dies, withdraws consent, or is lost to follow-up during the period of the SN event, the DSN will be calculated as described above, but the end date will be the last ANC assessment before the end of the study.

Overall DSN (days) during treatment is the median DSN value for all cycles and the following data handling rules will be applied:

- If a patient 's SN event duration value is censored for all cycles, the patient' s median DSN value will be the median censored value and will be considered censored;
- If a patient 's partial cycle SN time duration value is a censored value, the Kaplan-Meier method will be used to estimate the median DSN value for that patient, which is the observed value;
- ➤ If a patient 's median DSN value cannot be calculated (eg, has ≤ 2 DSN values), the longest DSN value across all cycles (whether censored or not) will be used as the median value, but the corresponding censoring flag will be included in the analysis.

Kaplan-Meier methods will be used to estimate 25%, median, and 75% time (days) of the duration of SN and 95% confidence intervals (days) will be provided. Adjusted hazard ratio (HR) and its 95% CI between the two treatments (Trilaciclib versus placebo) will be calculated from a stratified Cox proportional hazard model with treatment group and randomization stratification factors based on Interactive Response Technology (IRT) as fixed effects. Stratification will be combined or reduced appropriately if the number of patients within a stratum is too small. Two-sided p-values will be calculated from stratified log-rank tests.

Confidential

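### Strategy 2, named as the stability check on Cycle 1 DSN, drops every patient without SN, so its result cannot be read as evidence on the stability of the primary analysis

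*SAP*

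**What the plan says.** SAP 4.4.1 sets the roles: "Strategy 1 is the primary analysis and Strategy 2 is the supportive sensitivity analysis". SAP 4.9 repeats that Strategy 2 checks the stability of the Strategy 1 result for Cycle 1 DSN.

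- **Patients without SN.** Strategy 1 (SAP 4.4.1.1) keeps them: "If a patient does not experience any SN during the cycle, DSN will be counted as 0 for that cycle". Strategy 2 (SAP 4.4.1.2) removes them: "Patients will not be included in the analysis if they does not experience any SN during this period".
- **What the heading announces.** "Strategy 2: Missing ANC values not imputed, censored handling unresolved SN". It does not mention a change of population.
- **End dates.** For SN unresolved at cycle end, Strategy 1 uses the cycle end. Under Strategy 2 "the end date will be the end date of the cycle or the last contact date, whichever occurs first". For death, Strategy 1 calculates DSN as usual "but the end date is the date of death", while Strategy 2 stops at the last ANC. Withdrawal and loss to follow-up stop at the last ANC in both.
- **Test.** Strategy 1 uses nonparametric ANCOVA. Strategy 2 uses Kaplan-Meier and a stratified Cox model, and "Two-sided p-values will be calculated from stratified log-rank tests".
- **Variable.** Just before the Strategy 2 test, the SAP adds "Overall DSN (days) during treatment is the median DSN value for all cycles", with its own censoring rules. It does not say whether the test uses this or Cycle 1 DSN.

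**The concern.** A stability check should hold the question fixed and vary one assumption. Here the announced assumption, the handling of unresolved SN, changes little, while three larger things change with it: who is analysed, what is estimated and how it is tested.

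The exclusion matters most. SN in Cycle 1 occurs after randomisation, and trilaciclib is meant to prevent it. Patients with SN in the two arms are therefore not randomised groups. Removing the zeros also removes the part of the endpoint on which the sample size was built, since SAP 2.2 derives both Poisson means from the proportion without SN.

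Followed as written, Strategy 2 asks whether episodes are shorter among patients who still had SN. A report could present a null answer as lack of robustness, or a significant one as confirmation. Neither would follow.

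**Working it through.** **Inputs.** SAP 2.2: planned Cycle 1 SN rates of 10% (trilaciclib) and 45% (placebo); integrated rates of 6.7% and 49.6%; 35 per group for about 95% power; 12% dropout; 40 per group enrolled. Protocol Table 3, integrated analysis: Cycle 1 DSN mean (SD) 4 (5.1) on placebo and 0 (1.8) on trilaciclib.

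**1. The plan's own figure.** −ln(0.90) = 0.105 and −ln(0.55) = 0.598. In 10,000 simulated trials at 35 per group, the two-sided Wilcoxon test has 94.5 to 94.9% power. The stated 95% is reproduced, and 70/0.88 = 79.5 rounds up to 80. At 40 per group, power is about 97%.

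**2. Who remains, if Strategy 2 is applied to Cycle 1.** 40 × 0.10 = 4 and 40 × 0.45 = 18, so 22 of 80 remain and 72.5% are dropped. With X binomial, P(X ≤ 3; 40, 0.10) = 42%. At the integrated 6.7%, the expected trilaciclib count is 2.7 and P(X ≤ 3) = 72%.

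**3. Under the plan's Poisson model.** Mean DSN given SN is 0.105/0.10 = 1.05 days against 0.598/0.45 = 1.33 days. The SN-only log-rank (unstratified, uncensored) is significant in 1.5% of trials at 35 per group and about 1.8% at 40. When the all-patient test is significant, the SN-only test is not in 98 to 99% of trials.

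**4. With longer episodes.** The documents give no distribution of episode length, so these are assumptions.
- Placebo: 4/0.496 = 8.06 days, with SD √((5.1² + 4²)/0.496 − 8.06²) = 4.43.
- Trilaciclib: SD given SN = √((1.8² + (0.067m)²)/0.067 − m²), which gives 3.84, 5.00 and 5.78 at m = 6, 5 and 4 days.

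Lengths were drawn as 1 + negative binomial, capped at 36 days, with 4,000 trials of 40 per arm. The ranges cover three choices of trilaciclib SD: the value above, 4.43, or scaled to the mean. Wilcoxon stands in for the nonparametric ANCOVA.

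| SN rates | Episode length (days) | SN-only log-rank | All-patient Wilcoxon |
|---|---|---|---|
| 10% vs 45% | 6 vs 8 | 22–26% | 97% |
| 10% vs 45% | 5 vs 8 | 39–43% | 97% |
| 10% vs 45% | 4 vs 8 | 56–62% | 98% |
| 45% vs 45% | 4 vs 8 | 64–94% | 18–19% |

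The SN-only column depends on the assumed spread. With 1 + Poisson lengths (placebo SD √7 = 2.65, below the 4.43 implied by Table 3), 5 vs 8 days gives about 66%. A 3,000-trial check at 4 vs 8 days gives about 86%.

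**5. Could episodes be equally long in both arms?** With rounding, placebo lies between 3.5/0.496 = 7.1 and 4.5/0.496 = 9.1 days. Trilaciclib is at most √((1.85² + 0.5²)/0.067) = 7.4 days. Equal lengths near 7.1 to 7.4 days are not strictly excluded, and the SN-only test would then have no true difference to find.

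**6. How many cases the announced change touches.** Protocol 5.4.2 requires neutrophils of at least 1.5 × 10⁹/L before Cycle 2 dosing, and SAP 4.1 ends Cycle 1 when Cycle 2 starts. Unresolved SN is therefore largely confined to patients who never start Cycle 2, and few are expected.

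**The case against.** **Strategy 2 is not empty.** It does treat unresolved SN differently, and it describes episode length given SN. This stands. A reader might infer that Strategy 2 is uninformative altogether, and the text does not support that. What is lost is attribution: its result cannot be traced to the rule it claims to vary.

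**The exclusion is written down.** It is explicit in SAP 4.4.1.2, though absent from the heading, and no decision rule depends on Strategy 2. Misreading is a risk, not a certainty.

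**Other supports are planned.** SAP 4.9 adds a split by G-CSF use and further analyses as needed. SAP 4.4 allows a PPS analysis when PPS and FAS differ by more than 10%. SAP 4.4.2.1 tests SN incidence and includes its own exact CMH stability check. Incidence and SN-only duration can be read as two parts of a zero-heavy endpoint. A reader might infer that the primary result has no other support, and that would be wrong. Still, none of these keeps all FAS patients and varies only the unresolved-SN rule.

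**Stratification.** It is tempting to argue that eight strata would leave the SN-only log-rank almost no usable data. The SAP allows small strata to be combined or reduced, so no such argument is made here.

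**A clean rerun will rarely differ.** This also stands. With zeros kept, 5 vs 8 days, and 5 to 20% of SN patients assumed unresolved (about 1 to 4 patients), last-ANC, cycle-end and worst-rank rules were each significant in 97 to 98% of 6,000 trials and agreed in at least 99%. The main gain is removing a misleading label.

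**Conclusion.** The point holds. As written, Strategy 2 cannot serve as the stability check that SAP 4.4.1 and 4.9 call it. It changes population, estimand and test together and conditions on an outcome that treatment is expected to reduce.

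On the Cycle 1 reading at the planned rates, about 4 against 18 patients remain. The SN-only test would be significant in about 2% of trials under the plan's Poisson model. It would be roughly 20 to 65% for assumed lengths of 4 to 6 against 8 days with a spread compatible with Table 3, and higher if lengths vary less. The all-patient test is significant in about 97 to 98% throughout. With equal SN rates and shorter episodes on trilaciclib, the pattern reverses. These percentages illustrate the mismatch and are not forecasts.

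The untested-variable question is more than cosmetic. If the test uses the all-cycle median DSN, the check leaves Cycle 1 altogether and the counts above do not apply. The SAP does not settle which is meant, although its stated purpose points to Cycle 1. Either way, patients without SN are excluded.

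A reader might infer that the primary analysis is in doubt. The documents do not support that: Strategy 1 keeps every FAS patient and is unaffected.

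**What to change.** 1. In SAP 4.4.1.2 and 4.9, define the stability check as a rerun of the Strategy 1 nonparametric ANCOVA on Cycle 1 DSN in all FAS patients, with DSN = 0 kept. Change only the end-date or rank rule for SN not resolved in Cycle 1, including death, withdrawal and loss to follow-up.
2. Keep the SN-only Kaplan-Meier, Cox and log-rank output, but label it a description of episode length conditional on SN and remove the stability wording.
3. State next to the log-rank and Cox text whether the variable is Cycle 1 DSN or the all-cycle overall DSN.

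The cost is SAP wording and one or two extra runs of the primary model. No new data are needed and the primary analysis does not change.
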